3.3 Benefit Risk Assessment

During the hypoglycemic clamp procedures, plasma glucose (PG) levels will be closely monitored and glucose infused, if necessary, to prevent PG dropping below the target values. Should the symptoms of hypoglycemia become unacceptable, glucose will be infused to increase PG. Vital signs and continuous electrocardiogram (ECG) will be monitored during the clamp procedures and the clamp will be terminated should the patient experience symptoms of cardiovascular stress (tachycardia, bradycardia, or other relevant changes in ECG), or neurological symptoms related to neuroglucopenia neuroglycopenia.

4. Objectives and Endpoints

Table GPHG. 1. Objectives and Endpoints

Objectives	Endpoints

Secondary
 
To compare the effect of tirzepatide 15 mg QW and placebo in T2DM patients following 12 weeks of treatment on:
 
Other counter-regulatory hormone responses during hypoglycemia, insulin and C-peptide
	
 Change in mean glucagon concentration from target PG concentration of 100 mg/dL to 63 mg/dL and to recovery (PG concentration 72 mg/dL) from induced hypoglycemia Change in mean glucagon concentration from ambient PG to target PG concentrations of 100, 63, and 45 mg/dL, and to recovery (PG concentration 72 mg/dL) from induced hypoglycemia Change in mean insulin, C-peptide, growth hormone, cortisol, adrenaline, and noradrenaline concentrations from target PG concentration of 100 mg/dL to 63 and 45 mg/dL, and to recovery (PG concentration 72 mg/dL) from induced hypoglycemia

5. Study Design

5.1 Overall Design

Eligibility for this study will be assessed at the screening (Visit 1) up to 17 days (Day 14 ± 3) prior to enrollment and confirmed at the beginning of the lead-in period (Visit 2); 10 to 4 days prior to randomization (Day 7 ± 3) when laboratory test results are available. After eligibility is confirmed at Visit 2, patients will receive training and information on how to subsequently monitor their own diabetes condition. Where applicable, patients will be required to undergo a washout of OAMs other than metformin between Visit 2 and Visit 3 (refer to Section 5.1.1 for details).

[figure not shown]

Figure GPHG.1 Illustration of study design for Protocol I8F0MC-GPHG.

5.1.1. Screening, Lead-in and Randomization

Eligibility for this study will be assessed during the screening period (Visit 1). The patient will sign the informed consent form (ICF) before any study procedures are performed. Screening procedures will be performed according to Section 2 (Schedule of Activities). Final determination of eligibility will occur at the beginning of the lead-in period at Visit 2, after all screening results are available. Eligible patients are those with T2DM treated with diet, exercise, and metformin with or without one other allowed oral antidiabetic medication (OAM) as specified in Inclusion Criterion [2].

Eligibility for this study for patients on metformin only will be assessed at the screening (Visit 1) up to 17 days prior to enrollment (Day -14 ±3) and confirmed at the beginning of the lead-in period (Visit 2). Eligible patients treated with metformin only will proceed to Visit 3 after approximately 1-week lead-in.

Eligible patients who are, in addition to metformin, on 1 more OAM, will discontinue this OAM immediately after Visit 2 and will undergo a 4-week washout between Visit 2 and Visit 3. During this washout period, the investigator will perform appropriate surveillance of the patients (by telephone interview and additional CRU visits, if necessary, at the investigators discretion) to monitor the safety and glycemic control of the patients. Once the 4-week washout period is completed, patients will proceed to Visit 3. Upon entering the study, patients should remain on the same metformin dose throughout the course of the study. Between screening and randomization (Day 1) eligible patients should continue their prestudy therapy with metformin. Patients who do not comply with requirements regarding metformin dosing will be discontinued from the study prior to randomization. After randomization, the metformin dose can only be reduced in accordance with country-specific label to protect patient safety (see Section 7.7 [Concomitant Therapy] for further details).

Eligible patients will be trained on glucose monitoring and disease management procedures, glucometer use for self-monitoring of plasma glucose (SMPG), study diaries, and study procedures at the lead-in visit (Visit 2) ~~10 to 4 days prior to randomization (Day -7 ±3)~~. Patients will start performing daily SMPG and record all results, including any hypoglycemia episode, in diaries as soon as their eligibility is confirmed at Visit 2. Patients will also follow the investigator's instructions related to any additional SMPG measurements, when judged to be needed for safety or eligibility assessments. All patients will be encouraged to maintain a stable diet and exercise plan throughout the course of the study.

5.1.3 Washout Between Treatment Periods

6. Study Population

Screening may occur up to ~~17~~ 45 days prior to enrollment (Day -14 ±3). All patients will then perform a lead-in start of randomization for patients treated with metformin and one other OAM, who are required to perform a washout during lead-in. For all other patients, screening may occur up to 17 days prior to randomization and perform a minimum 3-day lead-in. Patients who are not enrolled within these time periods may be subjected to an additional medical assessment and/or clinical measurements to confirm their eligibility. Patients will be dosed only if safety laboratory results not older than ~~17~~ 45 days are available.

6.1 Inclusion Criteria

- [2] Treated with diet and exercise and a stable dose of metformin (3 months prior to study entry) with or without 1 additional OAM other than metformin; doses of metformin will be considered stable if all prescribed doses for the previous 3 months were ± 850 mg from the most commonly prescribed dose; allowed OAMs, in combination with metformin are DPP-IV inhibitors, SGLT-2 inhibitors, acarbose, glinides and sulfonylureas; in patients with established cardiovascular disease who are treated with SGLT-2 inhibitors, this therapy should not be discontinued and therefore, these patients will NOT be eligible for participation in the trial.
- [3a] Have a hemoglobin A1c value at screening of $\ge 6.5\%$ and $\le 9.0\%$ (48 to 75 mmol/mol), if on metformin only;
- [3b] Have a hemoglobin A1c value at screening of $\ge 6.0\%$ and $\le 8.5\%$ (42 to 69 mmol/mol), if on metformin and 1 more allowed OAM;
- [5] Have a body mass index between 25.0 23.0 kg/m² and 40.0 45.0 kg/m², inclusive, at screening; are of stable weight ($\pm 5\%$) >3 months prior to screening; and agree not to initiate an intensive diet and/or exercise program during the study with the intent of reducing body weight other than lifestyle and dietary measures for diabetes treatment;

6.2 Exclusion Criteria

- [14] Have taken any glucose-lowering medications other than metformin anytime those indicated in Inclusion Criterion [2] during the last 3 months before screening or during the screening/lead-in period; short-term use of insulin (<14 days) for treatment of acute conditions is allowed in the 3-month period prior to entry and after randomization (see Section 7.7 Concomitant Therapy)

7.7 Concomitant Therapy

Glucose-Lowering Medications

Section 6.1 (Inclusion Criteria) and Section 6.2 (Exclusion Criteria) provide requirements regarding the use of glucose-lowering medications prior to entry and during the screening period. All patients in the study are required to be treated with stable doses of metformin for at least 3 months prior to study entry.

In addition, one additional OAM is allowed prior to randomization (Refer to Inclusion Criterion [2]), but must be discontinued after eligibility is confirmed at Visit 2, in which case a 4-week minimum washout is required.

Refer to Section 5.1.1 and 5.1.3 for additional information on washout period prior to starting study treatment.

Appendix 6 Hypoglycemic Clamp Procedure

Clamp Run-In Period

At 08:00 hours (10:00 hours latest), the insulin infusion rate will be increased to a constant rate of 2.5 mU/kg/min, based on patient body weight at Day 78 of each period.

Recovery Phase

If the PG has not reached ≥ 72 mg/dL (4.0 mmol/L) 45 minutes after termination of the constant insulin infusion, a constant glucose infusion (5.5 mg/kg/min, based on patient body weight at Day 78 of each period) will be initiated in order to increase the PG to 72 mg/dL (4.0 mmol/L). For medical reasons (e.g., if symptoms of hypoglycemia are unacceptable) the constant glucose infusion can be initiated earlier as judged by investigator.

Safety considerations for assessment plateaus

The clamp will be terminated for safety reasons should the patient experience symptoms of cardiovascular stress (tachycardia, bradycardia, or other relevant changes in ECG), or neurological symptoms related to ~~neuroglucopenia~~ neuroglycopenia, as judged by the investigator.

Approximate hour	Nominal timing	Procedure	Clamp glucose level	Blood sampling: - Glucagon - Fasting insulin - C-peptide - Growth hormone - Cortisol - Adrenaline	Hypoglycemia symptoms awareness Hypoglycemic symptoms score	Vital signs and ECG	Glucose and GIR recorded

Noradrenalin							
8:00	-1 hours to -30 minutes	Increase insulin flow (2.5 mU/kg/min) ($\pm 30\%$). Variable infusion of glucose targeting PG 100 mg/dL (5.5 mmol/L) ($\pm 30\%$)	100 mg/dL (5.5 mmol/L)			Start of continuous ECG measurement	Glucose every 5 to 30 minutes or more often as judged by investigator
8:30	-30 minutes	Insulin flow (2.5 mU/kg/min) ($\pm 30\%$). Variable infusion of glucose to maintain PG 100 mg/dL (5.5 mmol/L) ($\pm 10\%$)	100 mg/dL (5.5 mmol/L)	-20 minutes, -10 minutes, 0 minutes	-30 minutes 0 minutes	Vital signs -30 minutes 0 minutes 12-lead ECG -15 minutes	Glucose every 5 to 10 minutes or more often as judged by investigator

The assessments scheduled for the same time point on each plateau will be performed in following order (priority): blood glucose, vital signs, blood sampling, hypoglycemia symptoms awareness, hypoglycemic symptoms score.

The exact timing of each procedure will be recorded.

Leo Document ID = d5e67c84-0b39-49df-9af3-5300fc59bbee

Approver: PPD

Approval Date & Time: 16-Sep-2020 15:04:31 GMT

Signature meaning: Approved

Approver: PPD

Approval Date & Time: 17-Sep-2020 01:26:42 GMT

Signature meaning: Approved

Table GPHG.8.	Categorical Criteria for Treatment-Emergent Abnormal Blood Pressure and Pulse Measurements	31

Table of Contents

Figure		Page
Figure GPHG.1.	Illustration of study design for Protocol I8F-MC-GPHG.	11
Figure GPHG.2.	Hypoglycemic clamp.	12

Table of Contents

Appendix		Page
Appendix 1.	Search Criteria For Adverse Events of Special Safety Topics.....	37

3. Revision History

Statistical analysis plan (SAP) Version 1 was approved September 10, 2020.

This is SAP Version 2. The second version was approved before the final database lock. The overall changes made in this SAP are as follows:

- updated to address the changes made in Protocol Amendment (d)
- updated and clarified population for analyses
- added additional details for summaries of baseline patient characteristics, disposition, and concomitant therapy
- updated exposure and treatment compliance calculation, taking into account early termination
- added additional details for summaries of body weight, safety labs, and immunogenicity data
- updated and clarified details in treatment-emergent adverse event definition and special safety topics
- added additional details for summaries of vital signs and added criteria for treatment-emergent abnormal vital signs
- added algorithm details on lab measurement for values below or above the quantification limit, and
- made editorial changes and formatting corrections.

4. Study Objectives

Table GPHG.1 shows the objectives and endpoints of the study.

Table GPHG.1. Objectives and Endpoints

Objectives	Endpoints
Primary To compare the effect of tirzepatide 15 mg QW and placebo on glucagon response during hypoglycemia in T2DM patients following 12 weeks of treatment	Change in mean glucagon concentration during induced hypoglycemia from target PG concentration of 100 mg/dL to a nadir target of 45 mg/dL
Secondary To compare the effect of tirzepatide 15 mg QW and placebo in T2DM patients following 12 weeks of treatment on: 
 Other counter-regulatory hormone responses, and responses of insulin and C-peptide during hypoglycemia 	
 Change in mean glucagon concentration from target PG concentration of 100 mg/dL to 63 mg/dL and to recovery (PG concentration 72 mg/dL) from induced hypoglycemia Change in mean glucagon concentration from ambient PG to target PG concentrations of 100, 63, and 45 mg/dL, and to recovery (PG concentration 72 mg/dL) from induced hypoglycemia Change in mean insulin, C-peptide, growth hormone, cortisol, adrenaline, and noradrenaline concentrations from target PG concentration of 100 mg/dL to 63 and 45 mg/dL, and to recovery (PG concentration 72 mg/dL) from induced hypoglycemia
• Time to hypoglycemia recovery	
 Time from termination of insulin infusion at PG concentration of 45 mg/dL to reach recovery PG concentration (72 mg/dL) ($t_{PG \ nadir-72 \ mg/dL}$)
• Clinical hypoglycemia	
 Hypoglycemic symptoms score at PG concentrations of 100, 63, and 45 mg/dL and after recovery (PG concentration 72 mg/dL) from induced hypoglycemia Hypoglycemia awareness at PG concentrations of 100, 63, and 45 mg/dL and after recovery (PG concentration 72 mg/dL) from induced hypoglycemia
• Vital signs during hypoglycemia	
 Change in mean systolic and diastolic blood pressure and pulse rate from target PG concentration of 100 mg/dL, to 63, and 45 mg/dL, and to recovery (PG concentration 72 mg/dL) from induced hypoglycemia
• Additional safety and tolerability	
 AEs Incidence of hypoglycemia outside of the hypoglycemic clamps

Objectives	Endpoints

Exploratory
 
To compare the effect of tirzepatide 15 mg QW and placebo in T2DM patients following 12 weeks of treatment on:
 
 • Other hypoglycemic clamp and recovery parameters 	
 • Amount of insulin required to reach PG concentrations of 63 and 45 mg/dL from 100 mg/dL. • $AUC_{GIR,PG_nadir-72}$ mg/dL • Proportions of patients who require glucose infusion to attain recovery (PG concentration 72 mg/dL) and associated G_{tot} • PG achieved at the end of spontaneous recovery

 • Other safety parameters 	
 • Frequency of treatment-emergent anti-tirzepatide antibodies

Abbreviations: AE = adverse event; $AUC_{GIR,PG_nadir-72}$ mg/dL = area under the glucose infusion rate curve from time of termination of insulin infusion until recovery (PG concentration of 72 mg/dL); G_{tot} = total amount of glucose infused; PG = plasma glucose; QW = once-weekly; T2DM = type 2 diabetes mellitus.

Plasma glucose concentrations: 100 mg/dL = 5.5 mmol/L; 72 mg/dL = 4.0 mmol/L; 63 mg/dL = 3.5 mmol/L; 45 mg/dL = 2.5 mmol/L; ambient glucagon measured in the pre-prandial state prior to clamp initiation.

5. Study Design

5.1. Study Design and Treatment

This is a Phase 1, single-center, 2-period, crossover, randomized, patient- and investigator-blind study in patients with type 2 diabetes mellitus (T2DM). This study is designed to compare tirzepatide 15 mg once-weekly (QW) and placebo with respect to secretion of counter-regulatory hormones in response to a hypoglycemic stimulus and parameters of recovery from hypoglycemia.

Eligibility for this study will be assessed at screening (Visit 1) and confirmed at the beginning of the lead-in period (Visit 2). After eligibility is confirmed at Visit 2, patients will receive training and information on how to subsequently monitor their own diabetes condition. Where applicable, patients will be required to undergo a washout of oral antidiabetic medications (OAMs) other than metformin for at least 4 weeks between Visit 2 and Visit 3.

Following baseline assessments, eligible patients will be 1:1 randomized (Visit 3; Day 1) to treatment sequence. All patients will undergo 2 treatment periods (12 weeks of treatment), receiving tirzepatide in 1 period and placebo in the other, in a crossover fashion.

Tirzepatide 15 mg will be attained via step-wise dose escalation to reduce the risk of gastrointestinal adverse events (AE). Tirzepatide dosing will start at a dose of 2.5 mg QW for 2 weeks, followed by step-wise escalation to 5 mg QW for the next 2 weeks, 10 mg QW for the next 4 weeks, and 15 mg QW for the final 4 weeks.

There will be a washout period of at least 8 weeks (up to 10 weeks) between the last dose of study drug in Period 1 and the first dose in Period 2. The washout period will ensure sufficient washout of the study drug based on tirzepatide's elimination half-life of approximately 5 days.

At the end of each treatment period, patients will undergo a hypoglycemic clamp procedure (Day 79 ± 2 [clamp run-in period] and Day 80 ± 2 [hypoglycemic induction]). The hypoglycemic clamp procedure is detailed in protocol.

The planned study duration for an individual patient from screening through safety follow-up will be approximately 38 to 42 weeks.

Figure GPHG.1 illustrates the study design.

Figure GPHG.2 illustrates the hypoglycemic clamp procedure.

5.2. Determination of Sample Size

Approximately 38 patients are planned to be enrolled so that 30 patients complete the study assuming a 20% discontinuation rate. The calculation is based on the criterion that the width of the 95% confidence interval (CI) for the treatment comparison of the primary endpoint (change in glucagon from target plasma glucose concentration of 100 mg/dL to nadir target of 45 mg/dL) is within ± 23.65 pg/mL with approximately 80% probability, provided that the within-subject variability is 40 pg/mL (Korsatko et al. 2018).

[figure not shown]
[figure not shown]

Figure GPHG.1. Illustration of study design for Protocol I8F-MC-GPHG.

**Figure GPHG.2.****Hypoglycemic clamp.**

6. A Priori Statistical Methods

6.1. Populations for Analyses

For the purpose of analysis, [Table GPHG.2](#) defines 3 analysis sets.

Table GPHG.2. Analysis Populations/Data Sets

Population/Data Set	Definition
All randomized population	All patients who are randomly assigned to a treatment sequence.
Safety population	All randomized patients who are exposed to at least 1 dose of study drug (tirzepatide or placebo), regardless of whether they completed all protocol requirements.
PD analysis set *	Evaluable PD data from all randomized patients who are exposed to at least 1 dose of study drug and complete both hypoglycemic clamp procedures.

Abbreviations: PD = pharmacodynamic.

* Protocol deviations will be considered for their severity/impact and taken into consideration whether subjects should be excluded from PD analysis set for hypoglycemic clamp data related analyses.

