Tirzepatide, a dual GIPRA/GLP-1RA, is a 39-amino acid synthetic peptide. Its structure is based on the GIP sequence and includes a C20 fatty di-acid moiety which facilitates albumin binding and thus prolongs the duration of action. It has a chemical structure and pharmacologic profile that is distinct from the GLP-1RA due to the addition of GIP, which is unique among the marketed incretin mimetics. It is administered once-weekly (QW) by subcutaneous (SC) injection.

Tirzepatide is being developed as a therapy to improve glycemic control in adults with T2DM, as an adjunct to diet and exercise. Phase 3 studies are also planned for chronic weight management in obese/overweight adults and a Phase 2 study is planned for non-alcoholic steatohepatitis.

In a Phase 1 study (Coskun et al. 2018) that included single and multiple ascending dose (SAD, MAD) parts, tirzepatide has been administered as single SC doses up to 8 mg in healthy subjects. In the MAD part, higher doses up to 10 mg were attained in healthy subjects via dose escalation. Doses up to 15 mg were achieved in patients with T2DM via dose escalation. In this study, GI adverse events (AEs) (nausea, vomiting, diarrhea, and abdominal distension) and decreased appetite were the most frequently reported events by both healthy subjects and patients with T2DM and were dose related. Most AEs were mild in severity, a few were moderate, and none were reported as severe. During the SAD part of the study, the high incidence of GI AEs, notably vomiting, were considered to be dose limiting at the 8-mg dose; therefore, the 5-mg dose was considered the maximum tolerated dose. A dose-dependent increase in heart rate was detected for both healthy subjects and patients with T2DM who received tirzepatide, similar to what was observed with selective GLP-1 RAs. A few subjects experienced transient elevations in lipase and/or amylase levels, but these episodes were not associated with any relevant clinical outcomes.

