5.2. Number of Participants

Approximately 38 patients may be enrolled so that 30 complete the study. For the purposes of this study, a patient completes the study when all scheduled procedures through completion of the second hypoglycemic clamp procedure as per the Schedule of Activities (Section 2) have been finished.

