10.3.3. Pharmacodynamic Analyses

10.3.3.1. Pharmacodynamic Parameter Estimations

During the hypoglycemic clamp, for safety considerations, if the target PG concentrations are not achieved within 30 minutes of completion of the previous step, a higher PG concentration will be accepted as the PG concentration at which assessments are conducted. In case 45 mg/dL (2.5 mmol/L) cannot be reached or symptoms of hypoglycemia are unacceptable, nadir at a higher PG concentration will be accepted and data will be included in the analysis.

Mean glucagon, insulin, C-peptide, growth hormone, cortisol, adrenaline, and noradrenaline concentrations at target PG concentration clamp steps of 100, 63, and 45 mg/dL (5.5, 3.5, and 2.5 mmol/L) will be calculated from the 3 measurements taken during each clamp step. The concentrations are measured singly at ambient PG (glucagon only) and upon recovery to 72 mg/dL (4.0 mmol/L).

Mean systolic and diastolic blood pressure and pulse rate at target PG of 100, 63, and 45 mg/dL (5.5, 3.5, and 2.5 mmol/L) will be calculated using the average of the 2 measurements taken at each corresponding PG level. Blood pressure and pulse rate will be measured singly when recovery PG of 72 mg/dL (4.0 mmol/L) is reached.

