As soon as PG 72 mg/dL (4.0 mmol/L) is reached, assessments on the recovery time point will be performed. When the assessments are finished, PG will actively be raised to 100 mg/dL (5.5 mmol/L) by a variable glucose infusion and the whole clamp procedure terminated when deemed safe by the investigator. Thereafter, patients will receive a meal (containing carbohydrates) and will be discharged after having achieved stable medical conditions, as judged by the investigator.

Safety considerations for assessment plateaus

In case a patient's PG does not decrease from 100 mg/dL (5.5 mmol/L) to 63 mg/dL (3.5 mmol/L) within 30 minutes, the 63 mg/dL (3.5 mmol/L) assessment plateau will be initiated in any case 30 minutes after the end of the assessment plateau at 100 mg/dL (5.5 mmol/L).

In case a patient's PG does not decrease from 63 mg/dL (3.5 mmol/L) to 45 mg/dL (2.5 mmol/L) within 30 minutes, the 45 mg/dL (2.5 mmol/L) assessment plateau will be initiated in any case 30 minutes after the end of the assessment plateau at 63 mg/dL (3.5 mmol/L).

In the above cases, the glucose infusion should not be initiated at the start of the assessment plateaus to allow a further decrease in PG levels to the scheduled target PG levels.

Based on the clinical judgement of the investigator, the PG can be increased to euglycemia by a variable glucose infusion at any time during the whole clamp procedure.

From the start of the constant high insulin infusion rate until end of the recovery phase, PG measurements (using SuperGL device) have to be performed every 5 to 30 minutes or more often as judged by investigator.

After initiation of the constant high insulin infusion rate, potassium concentration will be measured at the discretion of the investigator and potassium substituted if necessary.

Electrocardiogram will be continuously monitored from start of the constant high insulin infusion rate until completion of the recovery phase. Twelve-lead ECG will be recorded within 15 minutes prior to start of the high insulin infusion rate, at timepoint 15 minutes (± 5 minutes) of assessment plateau 45 mg/dL (2.5 mmol/L) or nadir assessment plateau and before discharge.

The clamp will be terminated for safety reasons should the patient experience symptoms of cardiovascular stress (tachycardia, bradycardia, or other relevant changes in ECG), or neurological symptoms related to neuroglycopenia, as judged by the investigator.

[figure not shown]

Figure GPHG.2 Hypoglycemic clamp

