End of 45 mg/dL (nadir; 2.5 mmol/L)	J +30 minutes	Stop plateau nadir Start recovery
Reaching 72 mg/dL (4.0 mmol/L)	K minutes	Timepoint 4.0 mmol/L reached

* The PG level and duration of each plateau may vary due to patient's conditions as described in Safety Considerations for Assessment Plateaus in Appendix 6 of Protocol.

Counter-regulatory hormone responses, and responses of insulin and C-peptide to hypoglycemic clamp

Glucagon, growth hormone, cortisol, adrenaline, noradrenaline, insulin, and C-peptide concentrations at target PG levels of 100 mg/dL (5.5 mmol/L), 63 mg/dL (3.5 mmol/L), and 45 mg/dL (2.5 mmol/L) will be measured 3 times during each of these 3 plateaus (see [Table GPHG.4](#) for details).

- Mean concentrations at target PG levels of 100 mg/dL (5.5 mmol/L), 63 mg/dL (3.5 mmol/L), and 45 mg/dL (2.5 mmol/L) will be calculated from the 3 measurements taken during each of these 3 plateaus for PD analyses. If there is one missing measurement, the average value between 2 measurements will be used as the mean measurement. If there is only one value, it will be used as the measurement.

The concentrations are measured once at ambient PG (glucagon only) and upon recovery to 72 mg/dL (4.0 mmol/L) (see [Table GPHG.4](#) for details).

Table GPHG.4. Measurements of Glucagon, Insulin, C-peptide, Growth Hormone, Cortisol, Adrenaline, and Noradrenaline from Blood Sampling During Hypoglycemic Clamp Procedure on Day 79 and Day 80

Study Period Day	Clamp PG Level	Planned Timepoints* of Blood Sampling
Day 79		Only glucagon at ambient PG sample was measured in pre-prandial state prior to clamp initiation
Day 80	100 mg/dL (5.5 mmol/L)	-20 minutes -10 minutes 0 minutes
Day 80	63 mg/dL (3.5 mmol/L)	I + 10 minutes I + 20 minutes I + 30 minutes
Day 80	45 mg/dL (nadir; 2.5 mmol/L)	J + 10 minutes J + 20 minutes J + 30 minutes
Day 80	72 mg/dL (4.0 mmol/L)	K minutes

* The Planned Timepoints of blood sampling during clamp will be collected in eCRF.

Clinical hypoglycemia

Hypoglycemic symptom score

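### Does the undefined word *complete* in the PD analysis set leave the primary population open when a clamp is stopped for safety?

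*SAP*

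**What the plan says.** The primary model (SAP 6.9.2.1) is fitted in the PD analysis set, defined in SAP Table GPHG.2 as "Evaluable PD data from all randomized patients who are exposed to at least 1 dose of study drug and complete both hypoglycemic clamp procedures". Protocol 10.3 and SAP 8 use the same idea of completing both clamps, without defining it. Protocol 5.2 does not help: it says that "a patient completes the study when all scheduled procedures through completion of the second hypoglycemic clamp procedure" have been carried out, which rests on the same undefined completion.

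Protocol Appendix 6 provides for stopping early: "The clamp will be terminated for safety reasons should the patient experience symptoms of cardiovascular stress (tachycardia, bradycardia, or other relevant changes in ECG", or neuroglycopenic symptoms. It also describes the ordinary end of the procedure, after the recovery assessments: "PG will actively be raised to 100 mg/dL (5.5 mmol/L) by a variable glucose infusion and the whole clamp procedure terminated when deemed safe".

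Three rules bear on data from a shortened or modified clamp:

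- SAP 6.9.1, on plateau means: "If there is only one value, it will be used as the measurement".
- SAP Table GPHG.3, footnote: plateau level and duration may vary with the patient's "conditions as described in Safety Considerations for Assessment Plateaus in Appendix 6 of Protocol".
- Protocol 10.3.3.1, for a target not reached or symptoms that are unacceptable: "nadir at a higher PG concentration will be accepted and data will be included in the analysis". SAP 6.9.1 repeats this.

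**The concern.** The last primary glucagon sample is taken 30 minutes into the nadir plateau (J+30). The procedure then continues through recovery to 72 mg/dL (time K) and a raise to 100 mg/dL (time M), which the Appendix 6 table marks as the end of the clamp. A clamp stopped in recovery therefore holds all six primary samples and yet falls short of M. If *complete* means reaching M, that patient leaves the primary analysis, together with the other period's clamp.

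Two things would be at stake. First, two analysts could form different primary populations. Second, the patients concerned were stopped for signs of the condition under study, so dropping them might not be random. Stops could also differ by treatment: Protocol 3.2 reports that "A dose-dependent increase in heart rate was detected for both healthy subjects and patients with T2DM who received tirzepatide", and tachycardia is a named reason to stop.

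**Working it through.** **1. The text, by the stage at which a clamp is stopped**

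| Stop occurs | Primary samples available | What the documents say |
|---|---|---|
| Before J+10 | No nadir value | No endpoint on either reading |
| On the nadir plateau, after one or two samples | At least one nadir value | Appendix 6 holds the plateau for 30 minutes only if possible. SAP 6.9.1 accepts a single sample. The Table GPHG.3 footnote lets duration vary |
| In recovery, after J+30 | All six | Insulin has been off since J. Appendix 6 lets the investigator start the constant glucose infusion early for medical reasons, or restore euglycemia at any time |

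The first row is not in dispute. In the second, a short nadir plateau is a foreseen form of the clamp with a stated rule for its samples. In the third, what remains is mainly glucose infusion up to 72 and then 100 mg/dL, and bringing that forward is largely provided for. Appendix 6 also uses the same verb, terminated, for the normal end of the clamp and for a safety stop, so the word does not mark a clamp as incomplete.

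The disputed group shrinks further under Protocol 8.1.1. An event during a clamp may lead to permanent discontinuation of study drug, and such patients leave the study. If that happens in Period 1, there is no second clamp and no pair on either reading.

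**2. The planned precision**

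Inputs (SAP 5.2 and 6.2): within-subject SD 40 pg/mL, half-width 23.65 pg/mL, about 80% probability, two-sided 95% interval, 30 completers, 20% discontinuation.

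- Standard error = 40 × √(2/30) = 10.33 pg/mL.
- Expected half-width = t(0.975, 28) × 10.33 = 2.048 × 10.33 = 21.16 pg/mL.
- P(half-width ≤ 23.65) = P(χ² on 28 df ≤ 28 × (23.65/21.16)²) = 83.0%.
- With 29 pairs this is 78.6%, so 30 is the smallest number reaching 80%.
- 30/(1 − 0.20) = 37.5, rounded up to 38.

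The plan's 30 and 38 reproduce. A fall below 80% through stopped clamps would need those patients to count towards the 30 completers and then be dropped as not having completed, which uses the word in two opposite senses. On the strict reading they are not completers under Protocol 5.2 either, and they fall within the discontinuation allowance (38 − 30 = 8 patients). On the looser reading they are completers and are analysed.

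**3. Bias under the strict reading**

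The documents give no rate of stopped clamps, no between-patient SD and no link between stopping and glucagon response. An extreme case can be worked on assumptions: a share q of tirzepatide clamps is stopped, none on placebo, exactly the lowest glucagon responders are stopped, and every such patient is dropped. With between-patient SD B,

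bias = [1600/√(1600 + B²)] × φ(z_q)/(1 − q).

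- q = 0.05, B = 60: 22.19 × 0.1086 = 2.4 pg/mL.
- q = 0.10, B = 60: 22.19 × 0.195 = 4.3 pg/mL; B = 20: 35.78 × 0.195 = 7.0 pg/mL.
- q = 0.15, B = 20: 35.78 × 0.274 = 9.8 pg/mL.

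All are below the standard error of 10.33. The sign reverses if the highest responders are stopped, and the bias is zero if stopping is unrelated to glucagon response. These are not estimates of what the trial would show.

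**The case for a change.** The strongest case for a change is that none of the neighbouring rules strictly settles membership. The higher-nadir rule concerns the glucose level at which the plateau is held, not a terminated clamp. The single-sample rule says how to derive a value, not who is in the set. The footnote to Table GPHG.2 covers protocol deviations, and a safety stop follows the protocol. Dropping a patient with all six samples because of a later event would also discard data that need no missing-data assumption, and one sentence written before unblinding would remove any choice.

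What stands is that the two words are undefined and the status of a stopped clamp is not stated. What does not stand is that SAP 6.1 literally excludes such patients: that takes one meaning of an undefined word and calls it the text. Each rule alone is only adjacent, but together they point one way, to using observed plateau samples. The treatment-imbalance argument is also incomplete. It runs through heart rate, whereas bias in the primary endpoint needs stopping to depend on glucagon response, and no document makes that link.

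**Conclusion.** No change is needed. The undefined wording is a gap in detail. An analyst who reads SAP 6.1 with SAP 6.9.1 and Protocol Appendix 6 would most likely keep any pair with at least one glucagon value on the 100 mg/dL plateau and one on the nadir plateau in both periods. A written definition would say the same, so the primary analysis would probably be unchanged. Writing it down before unblinding would be harmless but optional.

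The remaining group is narrow: clamps stopped after at least one nadir sample and before the procedural end, in patients who also have endpoint data from the other period. Appendix 6 already records step end times and exact procedure times, so any such clamp can be identified when the set is formed.

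No bias figure can be drawn from the documents. Even the extreme illustration stays under one standard error, and the planned precision is unaffected when *complete* is read consistently. The conclusion assumes that analysts follow the lean of the surrounding rules and settle membership before treatment codes are known.
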